6.10.1 Definitions

Adverse event means any untoward medical occurrence associated with the use of a drug in humans, whether or not considered drug related.

Life-threatening adverse event or life-threatening suspected adverse reaction: An adverse event or suspected adverse reaction is considered "life-threatening" if, in the view of either the investigator or sponsor, its occurrence places the patient or subject at immediate risk of death. It does not include an adverse event or suspected adverse reaction that, had it occurred in a more severe form, might have caused death.

Serious adverse event or serious suspected adverse reaction: An adverse event or suspected adverse reaction is considered "serious" if, in the view of either the investigator or sponsor, it results in any of the following outcomes: Death, a life-threatening adverse event, inpatient hospitalization or prolongation of existing hospitalization, a persistent or significant incapacity or substantial disruption of the ability to conduct normal life functions, or a congenital anomaly/birth defect. Important medical events that may not result in death, be life-threatening, or require hospitalization may be considered serious when, based upon appropriate medical judgment, they may jeopardize the patient or subject and may require medical or surgical intervention to prevent one of the outcomes listed in this definition. Examples of such medical events include allergic bronchospasm requiring intensive treatment in an emergency room or at home, blood dyscrasias or convulsions that do not result in inpatient hospitalization, or the development of drug dependency or drug abuse.

Suspected adverse reaction means any adverse event for which there is a reasonable possibility that the drug caused the adverse event. For the purposes of IND safety reporting, "reasonable possibility" means there is evidence to suggest a causal relationship between the drug and the adverse event. Suspected adverse reaction implies a lesser degree of certainty about causality than adverse reaction, which means any adverse event caused by a drug.

Unexpected adverse event or unexpected suspected adverse reaction: An adverse event or suspected adverse reaction is considered "unexpected" if it is not listed in the investigator brochure or is not listed at the specificity or severity that has been observed; or, if an investigator brochure is not required or available, is not consistent with the risk information described in the general investigational plan or elsewhere in the current application, as amended. For example, under this definition, hepatic necrosis would be unexpected (by virtue of greater severity) if the investigator brochure referred only to elevated hepatic enzymes or hepatitis. Similarly, cerebral thromboembolism and cerebral vasculitis would be unexpected (by virtue of greater specificity) if the investigator brochure listed only cerebral vascular accidents. "Unexpected", as used in this definition, also refers to adverse events or suspected adverse reactions that are mentioned in the investigator brochure as occurring with a class of drugs or as anticipated from the pharmacological properties of the drug, but are not specifically mentioned as occurring with the particular drug under investigation.

6.10.2 Monitoring for adverse events

Adverse events will be recorded on study data forms whether or not they are thought to be associated with the study or with the study drug. Adverse events may be discovered during regularly scheduled visits or through unscheduled patient contacts between visits. Summary data on adverse events will be monitored by the DSMB quarterly and at its semiannual meetings or more frequently, as needed. These summaries will include analyses comparing rates of adverse events by treatment group, by clinic, or in other subgroups requested by the DSMB. Where applicable, signs and symptoms associated with the adverse event will be graded as to severity by the clinical site staff as mild, moderate, or severe using Version 3.0 of the National Cancer Institute's Common Terminology Criteria for Adverse Events (CTCAE).⁸¹

After each DSMB meeting, the NIDDK will issue a written summary of the review of the study data, including adverse events, for transmission to the IRBs at each of the study centers. Analyses or listings of adverse events will not be provided to the IRBs; however, adverse events involving unanticipated problems involving risks to participants, or breaches of protocol which might entail risk to participants must be reported to local IRBs as soon as possible after they are discovered. Each participating center is responsible for ensuring that all local IRB requirements for reporting adverse events are met.

A summary of adverse events will be reported to the FDA as part of the IND annual report.

6.10.3 Reporting serious adverse events

Serious adverse events (SAE) must be reported upon discovery at the clinical center. This will involve completing a data form describing the severity and details of the event, which must be submitted to the Data Coordinating Center within one business day for review by the Safety Officer.

If the SAE is **unexpected AND there is a reasonable possibility that the study drug caused the SAE**, then the clinical center must complete a data form for an IND Safety Report and submit it along with a narrative and a copy of the IRB report to the DCC. The DCC will submit a preliminary report to the NIDDK for review within three business days of receiving the SAE data form. The pharmaceutical manufacturer will also be notified within 7 days of the serious adverse event, if applicable. If NIDDK determines that the SAE requires an expedited IND Safety Report, the NIDDK program official or the NIDDK Regulatory Affairs Specialist will notify the FDA no more than 15 calendar days from the initial receipt of the SAE by the DCC (no later than 7 calendar days if the SAE is fatal or life threatening), if applicable. The clinical center investigator may also be responsible for completing an FDA MedWatch 3500 form and additional information for a follow-up SAE report as information becomes available. If the FDA determines that a change to the investigators brochure, IND or protocol is needed, the Data Coordinating Center will send a copy of the IND Safety Report to all clinical centers, with instructions to forward the report to their IRB.

The DCC will maintain a list of all SAEs for reporting and review at Steering Committee meetings and DSMB meetings. The DSMB will review each SAE report and provide comments to the NIDDK program official. If requested by any member of the DSMB, a teleconference will be scheduled to discuss the SAE and recommend any actions to the NIDDK sponsor. The clinical center must submit to the NIDDK and to the Data Coordinating Center a follow-up memo within one month of the SAE (and periodic updates if needed) to report the details of the disposition of the SAE.

6.11 Procedures for unmasking treatment assignment

Treatment assignments are double masked throughout the study until all data collection for the CyNCh trial has been completed (i.e., after completion of the 24 week post trial follow-up for all participants). Every effort will be made to maintain the masking throughout the study except in emergencies. The code of specific pharmacological treatment will not be broken without the knowledge of the clinical center's principal investigator and the study leadership.

Unmasking of study medication may occur under the following conditions:

- Severe allergic reaction (Stevens-Johnson Syndrome): Study medication is stopped indefinitely. The patient, primary care provider (PCP), and the investigator may be unmasked.
- **Pregnancy during the study:** Study medication will be stopped indefinitely, and the coded medication may be unmasked. The patient, PCP, and investigator will be notified of the associated risks of teratogenicity.
- **Development of hepatotoxicity:** Hepatotoxicity will be defined as the development of jaundice with a serum direct bilirubin of > 1.0 mg/dL and an increase in the baseline ALT and AST value that is two-fold or > 400 U/L during treatment. Study medication will be discontinued; however, there will be no unmasking until study conclusion.

The Data and Safety Monitoring Board will review all instances of unmasking that occur.

7. Statistical design and analysis

7.1 Primary hypothesis:

Cysteamine bitartrate DR at 9-12 mg/kg orally daily for 52 weeks is better than placebo in improving liver histologic parameters as measured by the NAFLD activity score in children with NAFLD.

Secondary aims:

- To assess safety and tolerability of cysteamine DR during the 52 week treatment period
- To assess the effect of cysteamine DR on:
 - Serum alanine aminotransferase (ALT), serum aspartate aminotransferase (AST) and serum γ -glutamyl transferase (GGT).
 - Liver fat as measured by MRI.
 - Markers of oxidation and anti-oxidant status: malondialdehyde, F2 alpha-isoprostane, total antioxidant capacity
 - o Insulin resistance
 - Anthropometrics
 - o Quality of Life
 - o Liver related symptoms

7.2 Outcome measures

Primary outcome measure:

The primary outcome measure, improvement in NAFLD from the start of treatment to the end of treatment at 52 weeks, is defined for each patient as:

- Improvement in NAS score by 2 or more points, and
- No worsening of the fibrosis score

Secondary outcome measures:

- *Conversion from a diagnosis of NASH to not-NASH.* For the subset of patients with NASH at enrollment, determine the proportion whose 52-week liver biopsy results in a centrally determined histological diagnosis of not-NASH
- *Change in NAS*. Change in NAS, is defined for each patient, as the difference in 52 week vs. baseline NAS scores
- *Specific histologic features.* Changes in specific histological scores, defined for each patient, as the difference in 52 weeks vs. baseline, in the following histological features from centrally scores liver biopsies:
 - **o** Fibrosis
 - o Steatosis
 - Lobular inflammation
 - Portal chronic inflammation
 - **o** Ballooning

Change from stage 1b to 1a fibrosis. For the subset of patients with stage 1b fibrosis at baseline, determine the proportion whose 52-week liver biopsy results in a centrally determined histological diagnosis of fibrosis 1a.

• *Serum aminotransferase*. Change in serum aminotransferase, is defined for each patient, as the difference in 52 week vs. baseline serum aminotransferase

- *Gamma-glutamyl transpeptidase*. Change in serum gamma-glutamyl transpeptidase, is defined for each patient, as the difference in 52 week vs. baseline serum gamma-glutamyl transpeptidase
- *MRI-determined hepatic fat fraction*. Change in MRI-determined hepatic fat fraction is defined for each patient, as the difference in 52 week vs. baseline MRI-determined hepatic fat fraction
- *Markers of oxidation and anti-oxidant status*. Change in markers of oxidation and anti-oxidant status, is defined for each patient, as the difference in 52 week vs. baseline values of the following markers:
 - o Malondialdehyde,
 - o F2alpha-isoprostane,
 - o Total antioxidant capacity, and
 - Oxidized LDL
- *Fasting insulin.* Change in fasting insulin, is defined for each patient, as the difference in 52 week vs. baseline fasting insulin
- *Fasting glucose*. Change in fasting glucose, is defined for each patient, as the difference in 52 week vs. baseline fasting glucose
- *Obesity measures.* Change in obesity measures, is defined for each patient, as the difference in 52 week vs. baseline values of the following obesity measures:
 - o Weight,
 - o Height,
 - o BMI,
 - Waist circumference
- *Pediatric Quality of Life*. Change in PedsQL score, is defined for each patient, as the difference in 52 week vs. baseline PedsQL score

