Current data suggest that NAFLD confers an increased risk for the development of cardiovascular disease, particularly through its association with metabolic syndrome. The key components of metabolic syndrome include central obesity, impaired glucose tolerance, elevated blood pressure, and dyslipidemia.¹⁷ A study demonstrated NAFLD to be more frequent among children with metabolic syndrome compared to children without metabolic syndrome.¹⁸ Of the 300 children evaluated, those with biopsy-proven NAFLD had a significantly greater cardiovascular risk profile. Higher values for fasting glucose, insulin, low-density lipoprotein cholesterol, triglycerides, and systolic blood pressure were observed in the NAFLD group. In a Swedish cohort study, patients with a history of steatohepatitis had significantly higher rates of cardiovascular disease and mortality when compared to patients with isolated steatosis.¹⁹ Identification of NAFLD should prompt consideration of cardiovascular health and relative risk reduction through lifestyle changes.

Children with NAFLD may have an increased risk for developing type 2 diabetes. In large studies of children with biopsy-proven NAFLD, 5 to 10% of children have type 2 diabetes at the time of diagnosis.^{7,20} Additionally, nearly 50% of children diagnosed with type 2 diabetes have suspected fatty liver based on ALT elevation.²¹ Progression to diabetes is important to understand from both preventive and therapeutic standpoints. In adults, the risk for development of diabetes may be as high as 20 to 25% over 5 years.^{22,23}

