4.3 Exclusion criteria

Exclusions will not be based upon gender, race, or ethnicity. Participants with a current history of the following conditions or any other health issues that make it unsafe for them to participate in the opinion of the investigators:

- Inflammatory bowel disease (if currently active) or prior resection of small intestine
- Heart disease (e.g., myocardial infarction, heart failure, unstable arrhythmias)
- Seizure disorders
- Active coagulopathy
- Gastrointestinal ulcers/bleeding
- Renal dysfunction with a creatinine clearance $< 90 \text{ mL/min/m}^2$
- History of active malignant disease requiring chemotherapy or radiation within the past 12 months prior to randomization

- History of significant alcohol intake (AUDIT questionnaire) or inability to quantify alcohol consumption
- Chronic use (defined as more than 2 consecutive weeks in the past year) of medications known to cause hepatic steatosis or steatohepatitis including:
 - o systemic glucocorticoids
 - o tetracycline
 - o anabolic steroids
 - o valproic acid
 - o salicylates
 - o tamoxifen,
- The use of other known hepatotoxins within 90 days of liver biopsy or within 120 days of randomization
- Initiation of medications with the intent to treat NAFLD/NASH in the time period following liver biopsy and prior to randomization
- History of total parenteral nutrition (TPN) use in the year prior to screening
- History of bariatric surgery or planning to undergo bariatric surgery during study duration
- Clinically significant depression (patients hospitalized for suicidal ideations or suicide attempts within the past 12 months)
- Any female who is nursing, planning a pregnancy, known or suspected to be pregnant, or who has a positive pregnancy screen
- Non-compensated liver disease with any one of the following hematologic, biochemical, and serological criteria on entry into protocol:
 - \circ Hemoglobin < 10 g/dL
 - White blood cell (WBC) < 3,500 cells/mm3 of blood
 - Neutrophil count < 1,500 cells/mm3 of blood
 - o Platelets < 130,000 cells/mm3 of blood
 - \circ Direct bilirubin > 1.0 mg/dL
 - \circ Total bilirubin >3 mg/dL
 - \circ Albumin < 3.2 g/dL
 - International normalized ratio (INR) > 1.4
- Poorly controlled diabetes mellitus (hemoglobin A1c (HbA1c) > 9%)
- Evidence of other chronic liver disease:
 - o Biopsy consistent with histological evidence of autoimmune hepatitis
 - Serum hepatitis B surface antigen (HBsAg) positive

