Determination of eligibility will be based mostly on chart review of standard of care tests and procedures that were completed before the first screening visit. The parent and child will sign the consent and assent at the first screening visit (or before) to obtain any tests and procedures needed to finalize eligibility after chart review and will undergo a history and physical examination including anthropometric assessments (body weight [kg], body height [m], body mass index [BMI], waist circumference [cm], and hip circumference [cm]) to identify other illnesses and contraindications for participation, including hepatosplenomegaly, peripheral manifestations of liver disease, ascites, wasting or fetor. History of prior liver biopsies and use of anti-NASH, anti-diabetic, statin, and fibrate medications in the three months prior to the biopsy will be obtained and recorded. Laboratory test results that need to be recorded from chart review or obtained as part of the screening visits include: tests for hepatitis B (HBsAg) and hepatitis C, anti-nuclear antibody (ANA), antimitochondrial antibody (AMA), anti-smooth muscle antibody (ASMA), ceruloplasmin, A1AT concentration, iron overload (iron, TIBC, and ferritin), fasting serum glucose, insulin, HgbA1C, P:\Shared\Doc\NASH\CyNCh\Protocol Confidential, September 06, 2013 not for distribution

complete blood count (CBC) with white blood cell differential, hepatic panel (total and direct bilirubin, AST, ALT, alkaline phosphatase, albumin, total protein, GGT, PT, INR), metabolic panel (sodium, potassium, chloride, carbon dioxide, calcium, BUN, creatinine, uric acid), and lipid panel (total cholesterol, triglyceride, LDL, HDL).

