5.10 Management of concomitant conditions

Hypertension, hyperlipidemia, and diabetes will be managed in conjunction with the patient's primary care physician according to the protocols described in the Standard of Care document prepared by the Pediatric Standard of Care Committee of NASH CRN.

Pregnancy will be managed according to the guidelines shown in section 6.10. In the event of major dermatological reactions such as generalized urticaria, bullous rashes, exfoliative dermatitis, or Stevens-Johnson Syndrome, study drug will be discontinued immediately and not restarted. For local skin reactions, study drug may be discontinued if the skin reactions are potentially drug related. If the rashes clear, the study drug may be restarted.

If local skin reactions recur with restarting the study drug, study drug should be discontinued. In cases where the study medication has been discontinued, the study drug will be unmasked and the participant, investigator, and the primary care provider will be notified in order to prevent future exposures.

6. Safety monitoring

6.1 Historical safety issues in children with nephropathic cystinosis taking immediate release cysteamine bitartrate (Cystagon[®]) capsules

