7.3 Statistical analysis

Primary outcome measure:

Statistical analyses for the primary hypothesis will follow the intention-to-treat paradigm, which means that all randomized patients with baseline and 52 week liver biopsies will be included in the treatment group to which they were assigned. Any randomized patient who does not have the requisite biopsies will be accounted for and compared by assigned treatment group.

Since the primary outcome measure, defined in Section 7.2, is a binary indicator of improvement in histologic activity score after 52 weeks of treatment compared to baseline and since the randomization is stratified by clinic, P-values will be derived from the Mantel-Haenszel $\chi 2$ test for stratified 2x2 tables. The proportion of patients improved in the group assigned to cysteamine DR will be compared to the group assigned to placebo and a two-tailed p-value of ≤ 0.05 will be considered statistically significant.

Secondary outcome measures:

Statistical analyses for the secondary measures that are continuous measures or scores will be carried out using separate bootstrapped mixed-effects-models corresponding to each individual change measure (defined in Section 7.2) as the response variable, with random effects for variation by clinic, and an indicator variable for comparing cysteamine DR (compared to placebo). The regression coefficient estimate for the indicator variable is the treatment effect for each secondary measure and is interpreted as the mean of the per-patient differences in each secondary outcome measure in the cysteamine DR group minus the corresponding mean differences in the placebo group. Statistical significance for each secondary treatment effect will be achieved if zero is not included in the nominal 95% bootstrapped confidence limits for each secondary measure. Bootstrapping with 2,000 replications will be performed to achieve 95% confidence limits that account for, in advance,

potential non-normality in the continuous secondary outcomes measures or scores. The bootstrapping estimation will be carried out using Stata software.

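### Change in fasting insulin is analysed without regard to insulin use, although children using insulin are eligible, so injected insulin may add noise of unknown size to this secondary outcome

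*Protocol*

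**What the plan says.** Insulin resistance is one of the secondary aims in Protocol section 7.1. Section 7.2 serves it with two measures, fasting insulin and fasting glucose. The insulin measure reads "Change in fasting insulin, is defined for each patient, as the difference in 52 week vs. baseline fasting insulin".

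The only diabetes criterion in section 4.3 is "Poorly controlled diabetes mellitus (hemoglobin A1c (HbA1c) > 9" percent). The list of medications that exclude a child does not name insulin or any other glucose-lowering drug. Use of such drugs is foreseen: at screening, "use of anti-NASH, anti-diabetic, statin, and fibrate medications in the three months prior to the biopsy will be obtained and recorded" (section 5.2). During the trial, "Hypertension, hyperlipidemia, and diabetes will be managed in conjunction with the patient's primary care physician", following a network standard-of-care document (section 5.10). On how common diabetes is, section 2.3 says that in large studies of biopsy-proven disease "5 to 10% of children have type 2 diabetes at the time of diagnosis".

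Section 7.3 fits a mixed model to each change score, "with random effects for variation by clinic, and an indicator variable for comparing cysteamine DR (compared to placebo"). The treatment coefficient "is interpreted as the mean of the per-patient differences in each secondary outcome measure in the cysteamine DR group minus" the corresponding placebo mean. The safeguard for non-normal data is the bootstrap: "Bootstrapping with 2,000 replications will be performed to achieve 95% confidence limits that account for, in advance". Randomization is stratified by center and body weight (section 3.2), not by diabetes or insulin use.

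**The concern.** Fasting insulin is informative about insulin resistance because it reflects how much insulin the child produces. In a child who injects insulin, the assay may also pick up the drug, and the value then depends partly on the prescription. If treatment is started or raised between baseline and week 52, measured insulin can rise while glucose falls, so the two glycemic outcomes point in opposite directions for a reason unrelated to the study drug.

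Because section 7.3 estimates a difference in arithmetic means, a few large changes carry full weight. The bootstrap addresses the shape of the distribution when the limits are formed. It leaves these values in the mean and does not narrow the interval. What is at stake is the precision and readability of one secondary result, not the primary outcome.

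**Working it through.** **The plan's own figures.** The protocol gives no SD, effect size or power for change in fasting insulin. Its only power statement concerns the primary outcome: 80 per group, 75% against 50% not improved, two-sided 0.05, 90% power. An uncorrected two-proportion calculation gives 91.2%, so that figure is reproduced, but it has no bearing here.

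**Inputs from the protocol**
- 160 children, 80 per group (section 7.5).
- Type 2 diabetes in 5% to 10% at diagnosis (section 2.3): 0.05 × 160 = 8 to 0.10 × 160 = 16 children.
- At most 10% missing at 52 weeks (section 7.4): 0.9 × 80 = 72 completers per arm.

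**Inputs that must be assumed.** The number of insulin users, the spread of insulin change in users and non-users, and whether the assay detects injected insulin or its analogues.

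**Widening of the standard error.** Let a share p of children have change-SD equal to k times the SD of the rest, with the same mean change. The variance is multiplied by (1 − p) + pk² = 1 + p(k² − 1), and the standard error by its square root.

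| p | children of 160 | k | variance factor | SE factor | effective sample |
|---|---|---|---|---|---|
| 1% | 1.6 | 3 | 1 + 0.01 × 8 = 1.08 | 1.04 | 1/1.08 = 93% |
| 2.5% | 4 | 5 | 1 + 0.025 × 24 = 1.60 | 1.26 | 1/1.60 = 63% |
| 5% | 8 | 5 | 1 + 0.05 × 24 = 2.20 | 1.48 | 1/2.20 = 45% |

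With 8 to 16 diabetic children, the last row needs half to all of them to be on insulin. The first row needs a tenth to a fifth.

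**The same calculation in absolute terms.** Take m users among 72 completers per arm, SD of change S in non-users and typical change U in users, all in assay units and all assumed. The SD is √[(1 − m/72)S² + (m/72)U²].
- Mild: S = 30, U = 50. One to four users per arm give SD 30.4 to 31.4, a loss of 2% to 9% of the effective sample.
- Middle: S = 20, U = 100, m = 2. SD = √(388.9 + 277.8) = 25.8, a factor of 1.29, and the loss is 1 − 400/666.7 = 40%. A true effect of 0.545 SD, detectable with 90% power without users, has 72% power. With m = 4 it has 57%.
- Extreme: S = 15, U = 200, m = 4. SD 49.3, a factor of 3.29.

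**One child's influence.** A change of 100 moves a 72-child arm mean by 100/72 = 1.4. At S = 20 the standard error of the arm difference is 20 × √(2/72) = 3.33, so the shift is 1.39/3.33 = 0.42 standard errors.

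**The case against.** The strongest objection is that the wording about each patient does not set an analysis population. It is a template that section 7.2 repeats for nearly every change measure, including MRI fat fraction, although MRI is optional and section 5.6 gives it its own eligibility list. Handling of concomitant drugs in a secondary outcome is often left to the statistical analysis plan, which is not shown. This stands in part: the phrase alone proves little. For MRI, however, other text narrows the set, and for insulin nothing does. Section 7.2 also sets baseline subsets itself, limiting NASH conversion to children with NASH at enrollment and the change from 1b to 1a to those with stage 1b at baseline. It is therefore the natural place for such a rule.

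The second objection concerns size. The 5% to 10% figure is diabetes in cited cohorts, not insulin use in this trial, and no SD is given. This stands fully. At the mild end the effect is trivial.

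The third is that randomization and masking balance baseline users in expectation, that stable use partly cancels in a change score, and that both arms follow the same standard-of-care document. This stands too. A reader might infer that insulin users bias the comparison or will swamp it. The documents support neither. They point to extra noise and chance imbalance, and a single change of 100 units shifts the difference by well under one standard error at the assumed SD of 20.

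**Conclusion.** The point holds as a modest one. As written, the outcome covers children who use insulin, and in them the measured value may not represent their own insulin output. The analysis has nothing that separates these values out.

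For assumed shares of 1% to 5% and SD ratios of 3 to 5, the standard error is about 4% to 48% wider. Other assumed inputs take the factor from 1.01 to above 3, which shows only that the protocol does not determine it. If few or no insulin users enrol, or the assay does not detect the injected product, little or nothing is lost. No bias is shown, and the primary outcome, sample size and safety assessment are unaffected.

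**What to change.** In section 7.2, restrict the fasting-insulin outcome to children not using insulin at baseline. Because the subset is fixed before randomization, the randomized comparison is kept, and the form matches what 7.2 already does for two histologic outcomes.

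Children who start insulin after randomization should stay in this comparison with their observed week-52 value. Earlier values should not be carried forward for them. That would impute after a post-randomization event and mix time points. It would also set the change to zero for a start before week 24, the first follow-up draw of fasting insulin. Some injected insulin can therefore still enter the outcome, so insulin and other glucose-lowering drug use should be reported by arm beside the insulin and glucose results. The analysis of all children should be shown as a sensitivity analysis.

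The cost is wording. Glucose-lowering drugs are already recorded at screening, and Appendix 10.2 schedules a review of concomitant medications at every visit. The downside is that a few children leave one secondary outcome.
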